12.3 Economic evaluation

12.3.1 Perspective and cost data collection

We will take an NHS provider perspective when considering the test results and associated costs and effects for the following diagnostic testing options:

1. Dipstick alone
2. Dipstick + 24 hour urine protein (gold standard)
3. Dipstick + SPCr (laboratory)
4. Dipstick + SACr (laboratory)
5. Dipstick + SPCr (point of care)
6. Dipstick + SACr (point of care)

We believe that the administration of the 24 hour urine protein, SPCr and SACr will be similar in costs. We will be able to verify whether this is true during our trial through a bottom up collection of data for a small subsample of tests at one study centre. We shall prospectively collect cost data on NHS resource use for this subsample through a time and motion study [20]. The main resources to be examined include:

1. the test
2. the equipment
3. staff time (lab technician, midwife, inpatient costs for 24-hour urine collection)

Study staff will observe and record the amount of staff time for each lab test. Information on unit costs will then be required to attach to each resource item in order that an overall cost per test can be calculated. Unit costs of the test and equipment will come from obtained from the company providing the test and equipment (Siemens Healthcare Diagnostics Limited, [name]). Staff time will be drawn from routine sources [21].

12.3.2 Economic analysis

The test that diagnoses PE and severe PE with the highest sensitivity and specificity is likely to be have both the lowest cost to the NHS and the best outcomes in terms of better case management and consequently, Quality Adjusted Life Years (QALYs) lost. The most accurate test will provide cost savings for the NHS as false negatives will be treated earlier. If SPCr or SACr demonstrate an increase in diagnostic accuracy, a consequence would be a decrease in unnecessary hospitalisation and outpatient visits and associated costs in the false positives. The key driver of the costs in the economic evaluation by Meads was the poor sensitivities and specificities of the tests [22]. Accordingly, our economic evaluation will improve upon their work through the inclusion of the new information on sensitivity and specificity provided by our trial while also examining the cost-effectiveness of test combinations, which was not considered in the HTA report due to lack of information [22].

We will construct a decision tree to extrapolate the costs and effects of the diagnostic test options beyond the time of our trial. This will build on the NICE Hypertension in Pregnancy Guideline to calculate the cost per QALY for each test [5]. The trial will provide us with the diagnostic accuracy of each test, which we will combine with data from the literature on QALYs lost and unit costs for true positives, true negatives, false positives and false negatives. True positives and true negatives will not require a QALY calculation. False positives will result in an unnecessary hospitalization for one day or an extra outpatient visit. While this could result in some decrease in QoL, NICE did not include this in their model due to the brevity of time it affects. Furthermore, our

lay representative maintained that for some of the women this hospitalisation would be a welcome rest from responsibilities. Consequently, we will calculate QALYs lost for false negatives only. Costs for each outcome will also build on the NICE model. Resource use will be prospectively collected for the women enrolled in the study. The main resources to be collected include:

1. Admissions to the hospital for labour and/or complications
2. Admissions to neonatal intensive care, high dependency units and special baby units.

Information on appropriate unit costs will then be attached to these resource use items. These costs will be collected from the participating hospital sites if possible and then supplemented with costs from routine sources, such as the Reference Costs Database [23].

Planned improvements to the NICE model include the examination of PE and severe PE as outcomes and trial data on prevalence of PE in women with gestational hypertension. Collecting data on the prevalence of PE is an important outcome of our trial as it was a key driver of results in the NICE model and also highly uncertain. We will also adapt the model to examine other relevant outcomes, such as cost per hospitalisation averted and cost per case of severe PE correctly identified.

[figure not shown]

Figure 3 Decision tree to compare the cost effectiveness of different screening options for PE in women with gestational hypertension

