5. BACKGROUND

5.1 Clinical Background

Preeclampsia is a multisystem disorder of pregnancy associated with raised blood pressure and proteinuria. Hypertensive disorders in pregnancy (HDP) remain the second leading cause of direct maternal deaths in the UK and account for 20% of all stillbirths [9, 10]. One in 5 women with hypertension is diagnosed with PE, resulting in complex treatment and substantial health care costs [5]. Women with severe PE require high dependency care. Preeclampsia is also responsible for significant infant morbidity related to fetal growth restriction and prematurity resulting in prolonged neonatal intensive care treatment and lifelong handicaps; the additional NHS costs to care for a preterm baby born before 33 weeks and 28 weeks are £61,509 and £94,190 respectively [5]. £939 million in extra costs for care of preterm babies per year in the NHS are linked to neonatal care such as incubation, and hospital readmissions [5].

The potential impact of early and accurate assessment of PE is enormous. The reliable diagnosis of significant proteinuria is critical in women with gestational hypertension because it distinguishes between those with PE from those with isolated hypertension; this distinction determines future monitoring and management. Furthermore, the determination of the most appropriate threshold for abnormal proteinuria that predicts clinical outcome helps to better focus resource on high risk women and reduce unnecessary iatrogenic intervention. Currently women with suspected PE undergo 24 hour proteinuria testing mostly as in-patients to evaluate the severity of the condition. The cost associated with 24-hour protein measurement and additional testing needs to be evaluated against identifying women with PE and avoiding the mortality, morbidity and costs associated with undiagnosed PE.

NICE acknowledges the paucity of evidence relating to the diagnosis of significant proteinuria and the unclear prognostic value of various urinary protein thresholds [5]. They have highlighted the need for “large, high-quality prospective studies comparing the various methods of measuring proteinuria (automated reagent-strip reading devices, urinary protein : creatinine ratio, urinary albumin : creatinine ratio, and 24-hour urine collection) in women with new-onset hypertensive disorders during pregnancy” [5].

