9.1.2 Inclusion criteria

Pregnant women aged between 16 and 45 years old who are more than 20 weeks gestation with confirmed gestational hypertension (systolic BP \geq 140 mmHg and/or diastolic BP \geq 90 mmHg) and trace or more proteinuria on automated dipstick urinalysis. This is below the threshold of 1+ considered “test positive” by NICE [5] and will thus allow exploration of the lower threshold for the index tests, i.e. below 300 mg/l protein.

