9.1.3 Exclusion criteria

Exclusion criteria: Women with gestational hypertension but no proteinuria on automated dipstick urinalysis, sustained proteinuria from before 20 weeks gestation, pre-existing renal disease, pre-gestational diabetes and chronic hypertension.

Figure 2: Study Patient Flow and Clinical Care

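### The economic model labels the trial's PE prevalence as prevalence in gestational hypertension, but the cohort excludes dipstick-negative women, so only prevalence and dipstick accuracy given trace or more can be estimated

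*Protocol*

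**What the plan says.** **The model population.** Protocol section 12.3.2 lists "trial data on prevalence of PE in women with gestational hypertension" among its improvements on the NICE model. It calls this prevalence an important trial outcome, because "it was a key driver of results in the NICE model and also highly uncertain". The Figure 3 caption describes a comparison of "different screening options for PE in women with gestational hypertension".

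**The options and their inputs.** Section 12.3.1 lists six options. The first is "Dipstick alone", and the other five add a second test to the dipstick. Under section 12.3.2 the trial supplies the accuracy of each test, and the literature supplies QALYs lost and unit costs.

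**The enrolled population.** Section 9.1.2 requires gestational hypertension together with "trace or more proteinuria on automated dipstick urinalysis". Section 9.1.3 excludes "Women with gestational hypertension but no proteinuria on automated dipstick urinalysis".

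**The related safeguard.** Section 12.3.4 names PE prevalence in gestational hypertension as an assumption to be varied in simple and probabilistic sensitivity analyses.

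**The concern.** The prevalence named in section 12.3.2 belongs to a wider group than the one enrolled. Women with gestational hypertension and a negative dipstick are in the first group and, by rule, not in the second. Section 7.4 provides for counting women who are eligible, approached and recruited. Dipstick-negative women are ineligible, so neither their number nor their PE status is recorded, and no outside source is named for either.

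The dipstick is also the entry step of all six options, yet its results are seen only from trace upwards.

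What is at stake is the economic part of the study (objectives 5 and 6): the reported prevalence, the absolute costs and QALY losses per woman, and the cost per correct diagnosis, if these are presented as results for gestational hypertension.

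**Working it through.** **1. The plan's own figure.** The protocol gives no PE prevalence for its cohort. The nearest figure is proxy severe PE in section 12.1: 78/500 = 15.6%, which reproduces. Its denominator is recruited women, who by the entry criteria have trace or more.

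**2. What can be estimated.** Let s be the share of gestational hypertension with trace or more, P the PE prevalence in that group, r the prevalence in dipstick-negative women, and π the prevalence in all gestational hypertension.

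- π = sP + (1 − s)r
- P/π = 1 / [s + (1 − s)r/P]

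The trial gives P but neither s nor r. The ratio exceeds 1 whenever r < P, and cannot exceed 1/s.

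**3. Direction.** Section 5.4 cites LR+ 4.27 and LR− 0.225 for the automated dipstick. I take the cut-off as 1+, which that sentence does not state.

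- Specificity = (4.27 − 1)/(4.27 − 0.225) = 0.808; sensitivity = 4.27 × (1 − 0.808) ≈ 0.818.
- At an assumed π of 20%, prevalence above the cut-off is 0.854/(0.854 + 0.8) = 51.6%, and below it 0.045/(0.045 + 0.8) = 5.3%.

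So removing dipstick-negative women should raise the observed prevalence.

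**4. Size, under assumptions.** The documents give neither dipstick accuracy at trace nor the dipstick-negative share.

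| Assumed inputs | Lowest P/π | Highest P/π |
|---|---|---|
| π 20%; sensitivity at trace 0.85–0.98, specificity at trace 0.4–0.7 | 0.170/(0.170 + 0.480) = 26%, ratio 1.31 | 0.196/(0.196 + 0.240) = 45%, ratio 2.25 |
| Dipstick-negative share 20–60%, r 0–10%, P 24.9–70.1% (the two assay proportions in section 5.4, used as a range) | 0.249/(0.8 × 0.249 + 0.2 × 0.10) = 1.14 | 1/0.4 = 2.5 |
| Dipstick-negative share 40–70%, r 0–5%, P 40–60% | 0.40/(0.6 × 0.40 + 0.4 × 0.05) = 0.40/0.26 = 1.54 | 0.40/(0.3 × 0.40) = 3.33 |

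Together these span about 1.1 to 3.3.

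**5. Dipstick accuracy.** At a trace cut-off every enrolled woman is positive, so sensitivity is 100% and specificity 0%. At 1+, with the trace-level accuracy assumed in the first row:

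- apparent sensitivity = 0.818/0.98 to 0.818/0.85 = 0.84 to 0.96, against 0.818 in the whole population;
- apparent specificity = 1 − 0.192/0.3 to 1 − 0.192/0.6 = 0.36 to 0.68, against 0.808.

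**6. Which outputs are affected.**

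- *False negatives per woman.* These drive QALY loss in section 12.3.2. Suppose a second test has sensitivity 83.6% (the pooled SPCr value in section 5.4) among women with trace or more. The trial-based figure is P × 0.164. The figure for all gestational hypertension is π × (1 − sensitivity at trace × 0.836). At 0.85/0.4 for trace sensitivity/specificity this is 0.262 × 0.164 = 43 per 1,000 against 0.2 × (1 − 0.711) = 58 per 1,000. At 0.98/0.7 it is 0.45 × 0.164 = 74 against 0.2 × (1 − 0.819) = 36. The absolute figure is wrong for the stated population, and its direction is not fixed: the higher prevalence pushes it up, and the unseen dipstick-negative cases push it down.
- *Incremental ratios.* If dipstick-zero women are handled alike in every option, they add nothing to the cost difference ΔC or the utility difference ΔU. The population differences are sΔC and sΔU, and their ratio is ΔC/ΔU, as in the cohort.
- *Mixing sources.* Applying the whole-population LR+ of 4.27 to the trial prevalence uses the dipstick twice. From P of 26.2% and 45% it gives 1.117/(1.117 + 0.738) = 60% and 1.92/(1.92 + 0.55) = 78%, where 51.6% is correct under the same assumptions.

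**The case against.** The best defence is that section 12.3.2 uses loose shorthand. Section 6 defines the study population with the dipstick criterion, section 12.1 speaks of gestational hypertension with suspected PE, and the tree itself is not visible in the text at hand. But section 9.1.3 uses gestational hypertension to include dipstick-negative women, and section 12.3.2 presents the prevalence as a trial outcome in its own right. The label needs correcting on either reading.

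Three stronger readings are tempting, and the documents do not support them.

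- *Every option's cost per QALY is distorted.* Section 12.3.4 defines an incremental ratio against 24-hour protein. If the second test follows a positive dipstick, and prevalence and accuracy both come from the cohort, dipstick-zero women cancel from it. This part of the defence stands. It would fail if whole-population dipstick accuracy were combined with the trial prevalence.
- *Option 1 cannot be evaluated at all.* Section 9.1.2 gives 1+ as the NICE positive threshold, so enrolled trace women with PE are observed false negatives. Accuracy at 1+ is estimable given trace or more; only unconditional accuracy is out of reach.
- *The overstatement can be read off the background figure.* Section 5.1 says "One in 5 women with hypertension is diagnosed with PE", which concerns hypertension in general. It is context, not a benchmark.

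The sensitivity analysis in section 12.3.4 is a partial safeguard. It could cover lower prevalences, but it does not correct the base case or supply the missing dipstick-negative results.

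**Conclusion.** The point holds. The trial estimates PE prevalence given trace or more, and section 12.3.2 assigns that estimate to gestational hypertension as a whole. It overstates the named quantity as long as PE is rarer in dipstick-negative women, which the likelihood ratios cited in section 5.4 support. The factor of about 1.1 to 3.3 rests wholly on assumed values for the dipstick-negative share, its PE prevalence and accuracy at trace.

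Absolute prevalence, per-woman costs and QALY loss, and cost per correct diagnosis would be wrong for the stated population. Incremental ratios may be unaffected under the two conditions above: dipstick-zero women handled identically, and prevalence and accuracy taken from the same cohort. The primary objective, sample size and accuracy analysis do not depend on this, so it is not a must-fix for the primary objective. It should still be settled before the model is built.

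**What to change.** In sections 12.3.1 and 12.3.2 and the Figure 3 caption:

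- define the base-case model population as gestational hypertension with trace or more on the automated dipstick, with 1+ or more as a second scenario;
- label the trial prevalence in the same terms;
- define option 1 as 1+ or more among women with trace or more.

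If a model of all gestational hypertension is also wanted, take the dipstick-negative share, its PE prevalence and unconditional dipstick accuracy from named external sources, with distributions in the probabilistic analysis. Do not apply a further whole-population dipstick step to the trial prevalence, which is already conditioned on the dipstick.

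The cost is wording and a few model inputs; recruitment and data collection are untouched. The downside is a narrower base-case claim.

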12.3.3 Discounting

The time horizon for the difference in costs and benefits will be over the lifetime of the mother and child as in the NICE model [5]. Many of the costs and benefits will be experienced in future years. Using discounting, adjustments will be made to reflect this differential timing. The base-case analysis will adhere to the Treasury recommendation of 3.5% for public sector projects.

12.3.4 Presentation of results and sensitivity analysis

The economic analysis will result in a cost per QALY for each screening option as calculated by the decision tree. Using the costs to the NHS and QALY loss calculated for each screening option, we can calculate the Incremental Cost-Effectiveness Ratio (ICER) with 24 hour urine protein as the comparator, where:

ICER = (Cost of regime A – Cost 24 hour urine protein)/ (Utility of regime A – Utility 24 hour urine protein).

The ICER will allow us to see the relationship between the mean difference in cost and the mean difference in benefits for each screening option. In this way, the cost per QALY of each index test can be compared to current treatment.

Simple and probabilistic sensitivity analyses will be employed to explore the robustness of these results to plausible variations in key assumptions, such as prevalence of PE in women with gestational hypertension.

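### The only ICERs specified compare each of the other five test options with 24-hour urine protein, and such ratios cannot show which of the six is best

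*Protocol*

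**What the plan says.** Protocol section 12.3.1 says the evaluation will consider "associated costs and effects for the following diagnostic testing options" and lists six: dipstick alone, and dipstick followed by 24-hour protein, laboratory SPCr, laboratory SACr, point-of-care SPCr or point-of-care SACr. The 24-hour option is labelled the gold standard.

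Section 12.3.4 plans a cost and a QALY loss for every option, and then: "we can calculate the Incremental Cost-Effectiveness Ratio (ICER) with 24 hour urine protein as the comparator". One formula is printed. For any regime A it divides the cost difference from 24-hour protein by the utility difference from 24-hour protein. The stated use is that "the cost per QALY of each index test can be compared to current treatment".

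On QALYs, section 12.3.2 says: "Consequently, we will calculate QALYs lost for false negatives only". The same section adds cost per hospitalisation averted and cost per severe PE case correctly identified, without an incremental rule for either. Section 12.3.4 plans simple and probabilistic sensitivity analyses, which vary assumptions such as prevalence and leave the comparator unchanged.

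**The concern.** The options are mutually exclusive. Choosing among them requires knowing what each more effective option costs over the next best alternative, not only over one fixed reference. A ratio against a common comparator answers a narrower question: is this option acceptable in place of 24-hour collection? Several options can pass that test together, and the size of the ratio does not order them.

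Section 6 makes replacement of 24-hour estimation by SPCr or SACr an objective, and section 5.1 says the study is to determine which measurement method is most accurate. The economic analysis will therefore be read for which test to adopt, and the specified ratios do not answer that.

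The sign of the ratio is a further difficulty. If the comparator loses no QALYs by construction, the other options can only match it or fall below it. The ratio is then undefined, or it has a meaning opposite to the usual cost per QALY gained.

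**Working it through.** The protocol gives no costs, QALY losses, ICERs or threshold, so there is no figure of its own to reproduce. All costs and QALY values below are assumptions chosen to test the rule. Write λ for the threshold in pounds per QALY.

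**1. Two cheaper, less effective tests, over a range of λ**

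Relative to 24-hour protein, A saves £100 and loses 0.002 QALY; B saves £150 and loses 0.005 QALY.

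- Section 12.3.4 ratio for A: (−100)/(−0.002) = £50,000 saved per QALY lost.
- Section 12.3.4 ratio for B: (−150)/(−0.005) = £30,000 saved per QALY lost.
- B against A: (150 − 100)/(0.005 − 0.002) = 50/0.003 = £16,667 saved per extra QALY lost.

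Net monetary benefit against 24-hour protein is saving − λ × QALYs lost:

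| λ (£) | A: 100 − 0.002λ | B: 150 − 0.005λ | Better |
|---|---|---|---|
| 10,000 | 80 | 100 | B |
| 16,667 | 66.7 | 66.7 | tie |
| 20,000 | 60 | 50 | A |
| 25,000 | 50 | 25 | A |
| 30,000 | 40 | 0 | A |

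Both pass at every λ below £30,000. The two common-comparator ratios stay at 50,000 and 30,000 throughout, while the best option changes at £16,667. That figure comes only from comparing B with A, which the protocol does not specify.

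**2. Two dearer, more effective tests**

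Assumed cost and QALY loss: 24-hour protein £200, 0.020; laboratory SPCr £210, 0.019; laboratory SACr £254, 0.017.

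- SPCr against 24-hour: 10/0.001 = £10,000 per QALY.
- SACr against 24-hour: 54/0.003 = £18,000 per QALY.
- SACr against SPCr: 44/0.002 = £22,000 per QALY.

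At λ = £20,000 both pass against 24-hour protein, but SACr fails against SPCr. Net benefit (−cost − λ × loss) is −200 − 400 = −600 for 24-hour, −210 − 380 = −590 for SPCr and −254 − 340 = −594 for SACr. SPCr is best, by £4 over SACr.

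**3. 24-hour protein itself dominated**

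Section 5.2 says 24-hour collection carries significant admission costs, so this case deserves a check. Assume 24-hour £400, 0.020; laboratory SPCr £150, 0.019; laboratory SACr £230, 0.017; point-of-care SACr £300, 0.0165.

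- Ratios against 24-hour: −250/0.001 = −250,000; −170/0.003 = −56,667; −100/0.0035 = −28,571.

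All three dominate 24-hour protein, and negative ratios have no useful order. Sequential ratios separate them: SACr against SPCr is 80/0.002 = £40,000, and point-of-care against laboratory SACr is 70/0.0005 = £140,000.

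**4. Sign of the utility difference**

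Section 7.2 defines the secondary outcome of PE by 24-hour protein at 300 mg/24 h. If the model scores tests against that definition at that threshold, the 24-hour option has no false negatives by construction. With QALYs lost for false negatives only (section 12.3.2), its loss is zero and every other option's loss is zero or more. Hence U(A) − U(24-hour) ≤ 0. With no false negatives under A, the denominator is zero. With some, and a lower cost, the ratio is positive but is a saving per QALY forgone, so a larger value is better.

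**The case against.** The best case for the plan has four parts.

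First, replacement of 24-hour protein is the stated objective, so a contrast with it is legitimate. That stands. The contrast belongs in the report; the difficulty is that it is the only ICER specified.

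Second, cost and QALY loss are planned for every option, so any pairwise ratio or net benefit can be derived later, and an analysis plan may do so. The first half stands and makes the fix cheap. But the protocol does more than leave the comparator open: it names one and prints the formula.

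Third, a careful reader of example 1 would know that a larger saving per QALY lost is better, and would choose A, the net-benefit winner at £20,000. This does not rescue the ratios. Below £16,667 they still favour A while B is better: at £10,000, 100 against 80.

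Fourth, the inputs are invented and the differences small. That stands. The examples show that the rule can fail to identify the best option; they do not estimate how often or by how much.

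A reader might also infer that 24-hour protein is treated as error-free throughout, so that every denominator is zero or negative. The protocol does not support this. Section 5.2 reports measurement errors in as many as 20% of patients and considers a spot test that predicts outcomes better. Section 12.3.2 allows for a gain in accuracy and makes severe PE a model outcome. The sign problem is therefore conditional on how PE is scored.

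**Conclusion.** The point holds in limited form. Section 12.3.4 specifies five ICERs, all against 24-hour protein, which is itself one of the six options. These can show which options are acceptable in place of 24-hour collection at a given threshold, but cannot identify the best of the six. That follows from the options being mutually exclusive and does not depend on the assumed numbers. The numbers only illustrate it: in example 1, both tests pass below £30,000 while the optimum switches at £16,667.

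It would go too far to say that the plan will recommend the wrong test. The protocol states no threshold and no rule for choosing by these ratios, so that outcome is possible but not shown. The zero or negative denominator applies only if PE is scored against the 24-hour threshold and the 24-hour option enters as error-free for it. Whether to give 24-hour protein an error rate is a separate modelling choice, outside this point.

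The matter affects the economic objectives, which are secondary. It does not touch recruitment, data collection or the primary accuracy analysis.

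**What to change.** Amend Protocol section 12.3.4 as follows:

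- Rank all six options by cost, remove those that are dominated or extendedly dominated, and report each remaining option's ICER against the next less costly option on the frontier.
- Report expected net monetary benefit for all six options, with acceptability curves over a range of thresholds, from the probabilistic analysis already planned.
- Keep the comparison with 24-hour protein as supplementary. For each option, show the cost and QALY differences with their signs beside the ratio, state when the ratio is a saving per QALY forgone, and print no ratio when the utility difference is zero.

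The cost is a wording change and a little more analysis. The model outputs are the same and no new data are needed.

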5.3 Summary of current evidence

Current recommendations for assessment of proteinuria vary. Recently published NICE guidelines in the UK suggest the use of automated reagent-strip reading device to detect proteinuria. In women with a result of 1+ or more, the use of spot SPCr or 24 hour urine collection is recommended to quantify proteinuria. Significant proteinuria is defined as SPCr greater than 30 mg/mmol or a validated 24-hour urine collection greater than 300 mg/24 hour. Where 24-hour urine collection is used to quantify proteinuria, a recognized method of evaluating completeness of the sample is recommended [5]. The Society of Obstetricians and Gynaecologists of Canada suggests using urinary dipstick testing to screen for proteinuria, with the definition of significant proteinuria similar to NICE guidelines [11]. The American College of Obstetricians and Gynaecologists consider 24 hour urine protein estimation of more than 300 mg as significant proteinuria for a diagnosis of PE [12].

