9. STUDY CONDUCT

All eligible women will be invited to participate at each site. Women will be given trial information by the research midwife and a Participant Information Sheet (PIS) to keep, and then subsequently recruited following obtaining written consent.

As part of routine clinical care women are asked to provide a urine sample for protein analysis. In those women who consent to taking part in this study, an aliquot of the spot urine sample will be collected and stored at -80°C. This spot urine will then be sent for a laboratory SPCr. Clinical management will be determined at this point based on the automated urine dipstick result and SPCr (as per routine practice). Women will then be asked to collect a 24 hour urine sample as either an in-patient or outpatient, dependent on the clinical care plan (as per NICE CG107) [5]. Those women with trace proteinuria and a SPCr <30mg/mmol (i.e. without clinical PE) will collect as an outpatient and those with a SPCr of >30 mg/mmol (i.e. with a clinical diagnosis of PE) will collect as an in-patient. An aliquot of this 24-hour urine sample will be stored at -80°C for secondary analysis. Clinical management will be determined from the automated dipstick, the local laboratory SPCr and /or the local laboratory 24 hour urine collection performed locally.

Immediately prior to delivery, a further spot sample of urine will be taken and stored for later analysis. This will allow the maximum proteinuria level to be calculated as well as the increase in proteinuria from initial presentation.

Women will be followed up until 6 weeks postnatal when their blood pressure and proteinuria results (from either hospital / primary care clinics) will confirm their pregnancy diagnosis. At this point a detailed collection of outcome data will be performed by the research midwife. Data will be abstracted from the hospital records for the maternal and neonatal outcomes at birth and discharge home.

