15.1 Participating sites

Sites participating in the project should:

- use NICE Hypertension in Pregnancy Guideline CG 107 for the management of hypertensive disorders in Pregnancy.

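### The protocol describes current care in two ways, and the only ICER reference, 24-hour urine protein, is called current treatment without settling which applies

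*Protocol*

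**What the plan says.** **Comparator and label.** Protocol section 12.3.4 states that "we can calculate the Incremental Cost-Effectiveness Ratio (ICER) with 24 hour urine protein as the comparator". It writes out the formula with the cost and utility of 24-hour protein as the reference terms, then concludes: "In this way, the cost per QALY of each index test can be compared to current treatment".

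**Statements on current care.**
- Section 5.1: "Currently women with suspected PE undergo 24 hour proteinuria testing mostly as in-patients to evaluate the severity of the condition". Section 5.2 likewise calls 24-hour protein the present gold standard.
- Section 5.3, on the NICE guideline for women at 1+ or more on dipstick: "the use of spot SPCr or 24 hour urine collection is recommended to quantify proteinuria".
- Section 9: "Clinical management will be determined at this point based on the automated urine dipstick result and SPCr (as per routine practice"). Trace proteinuria with SPCr below 30 mg/mmol then means outpatient collection, while "those with a SPCr of >30 mg/mmol (i.e. with a clinical diagnosis of PE) will collect as an in-patient". The same paragraph ends by resting management on the dipstick, the local SPCr and/or the local 24-hour result.
- Section 15.1 asks sites to "use NICE Hypertension in Pregnancy Guideline CG 107 for the management of hypertensive disorders in Pregnancy".

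**Options and outcomes.** Section 12.3.1 lists six testing options. Option 2 is dipstick plus 24-hour protein and option 3 is dipstick plus laboratory SPCr. It names in-patient cost of 24-hour collection as a resource item, but also expects the tests to cost about the same to administer. Section 12.3.2 adds as outcomes "cost per hospitalisation averted and cost per case of severe PE correctly identified".

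**The concern.** An economic result described as a comparison with current treatment will be read as the gain over what units do now. Under section 9, what units do first is dipstick and laboratory SPCr, and SPCr already sorts women into in-patient and outpatient collection. Under section 5.1, what they do is 24-hour testing, mostly in hospital. Section 12.3.4 adopts the second description without addressing the first.

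Laboratory SPCr therefore has two roles: part of routine practice in section 9, and in section 12.3 an option whose value is measured against current treatment. As written, no ICER for SACr or for a point-of-care test is taken against the pathway that section 9 calls routine. Such a test could look cost-saving against 24-hour protein while averting few or no further admissions beyond laboratory SPCr. Cost per hospitalisation averted is the outcome most exposed. Cost effectiveness is a stated secondary objective (section 6); the primary accuracy analysis is not affected.

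**Working it through.** The protocol states no ICER, cost or number of admissions averted, so there is no figure to reproduce. The check sets the sections side by side and then follows the algebra.

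**Step 1: do the sections agree?**

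| Section | What it treats as current or routine |
|---|---|
| 5.1 | 24-hour testing, mostly in-patient |
| 5.2 | 24-hour protein as gold standard |
| 5.3 | NICE: SPCr or 24-hour collection |
| 9, first statement | dipstick and SPCr |
| 9, later statement | dipstick, SPCr and/or 24-hour result |
| 12.3.4 | 24-hour protein |

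Sections 5.1 and 12.3.4 agree with each other. Section 9 differs from both, because it makes SPCr the routine first step that determines the setting. Section 5.3 is compatible with either. The site requirement in section 15.1 does not settle the matter, since the guideline as reported allows both tests.

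**Step 2: what does the reference do to admissions averted?** Per woman tested, let
- *a*(24) = share admitted under the 24-hour option, as costed in the model;
- *a*(S) = share admitted when SPCr decides;
- *a*(X) = share admitted under an index test X.

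Averted against 24-hour protein: *a*(24) − *a*(X).
Averted against option 3: *a*(S) − *a*(X).
Difference, the possible over-credit: [*a*(24) − *a*(X)] − [*a*(S) − *a*(X)] = *a*(24) − *a*(S).

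The over-credit does not depend on X. For a test that triages exactly as SPCr does, *a*(X) = *a*(S). It averts 0 against option 3 but is credited with *a*(24) − *a*(S) against 24-hour protein.

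**Step 3: what values can the over-credit take?**
- 24-hour option costed with section 9's pattern: *a*(24) = *a*(S), so the over-credit is 0.
- 24-hour option costed as mainly in-patient, following section 5.1: *a*(24) is larger than *a*(S) whenever SPCr sends some women to outpatient collection, so the over-credit is above 0.

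The protocol gives neither *a*(24) nor *a*(S). Section 12.3.1 points both ways, since it lists in-patient cost for the 24-hour test yet expects similar administration costs. Section 9's text gives a collection setting for trace women with SPCr below 30 and for women above 30. It gives none for women at 1+ or more with SPCr below 30, so even *a*(S) cannot be derived from it.

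**Step 4: is the missing contrast obtainable?** Yes. The tree gives a cost *C* and utility *U* for each option, and

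[*C*(X) − *C*(24)] − [*C*(3) − *C*(24)] = *C*(X) − *C*(3),

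with the same identity for *U*. The contrast with option 3 follows from quantities the plan already produces.

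**The case against.** The strongest reply is that 24-hour protein is the right comparator for the question asked. Objective 5 in section 6 concerns SPCr or SACr as a possible replacement for 24-hour estimation, and the ICER in section 12.3.4 answers that. Option 3 is in the model, so anyone can form the other contrast. Both points stand. They are reasons to keep the existing ICER and to see the repair as small. They do not justify the label, or the absence of a stated comparison with option 3.

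Three stronger readings are tempting, and the documents do not support them.

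- *That the 24-hour pathway is not used at the sites.* Sections 5.1 and 5.2 say it is, and section 9 lets management rest on the 24-hour result. Section 9 also does not have SPCr replace collection: participants are asked to collect, and SPCr decides where. What is shown is an inconsistent account of current care.
- *That savings will be wrongly credited.* This depends on how admissions under the 24-hour option are costed. With section 9's pattern nothing is over-credited. The care flow and decision-tree figures could not be seen and may settle this. Section 12.3.2 also ties unnecessary hospitalisation to false positives, a different route from admission for collection.
- *That the over-credit can be sized from the SPCr accuracy and assay prevalences in section 5.4.* Those yield the share of women below the SPCr threshold, not a share of admissions averted. Section 9 states outpatient collection only for trace women with SPCr below 30. The lower of the two prevalences comes from the Bradford assay, which section 8 does not list among the trial's methods.

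**Conclusion.** The contradiction is real and lies in the current text: section 12.3.4 (with section 5.1) and section 9 name different pathways as current care, and the only defined ICER reference rests on one of them. This is not a detail left to an analysis plan, because section 12.3.4 writes out the formula, names the reference and labels it.

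The consequence is conditional. The over-credit is *a*(24) − *a*(S) per woman: zero if the 24-hour option carries section 9's admission pattern, and positive if it is costed as mainly in-patient. No numerical upper figure can be drawn from the protocol. The conclusion assumes that the figures not shown do not already fix each option's admission pattern. If they do, the costing part of the point falls away, and the conflicting descriptions of current care remain.

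The point bears on how the cost-effectiveness results can be interpreted, not on the accuracy estimates or the choice of 24-hour protein as reference for the replacement question.

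**What to change.** 1. Reconcile sections 5.1, 5.3, 9, 12.3.1 and 12.3.4 on what current care is.
2. In section 12.3, state for each of the six options the admission pattern that is costed, including the setting of any 24-hour collection.
3. Keep the ICER against 24-hour protein. From the same decision tree, also report costs, QALYs and hospitalisations averted against option 3, dipstick plus laboratory SPCr.
4. Call 24-hour protein current treatment only if the reconciliation supports it; otherwise name it as the reference for the replacement objective.

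The cost is some rewording and one more reference column, with no new model arm. Apparent savings for SACr and point-of-care tests may be smaller against option 3. Because all participants are asked for a 24-hour collection, the trial data cannot be relied on to show how many women would be managed on SPCr alone. If that share is needed, it should come from site information or enter as a stated assumption with a range.
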